### **Data source**

This study will involve a secondary data analysis of COVID-19 patients' data from the ISeha Electronic health records. The following data will be used: patient demographic characteristics, clinical characteristics, and COVID-19 disease outcomes. The ISeha EHR data will be anonymized. Demographic and clinical data from eligible patients were recorded in ISeha electronic health records by medics on the ward. Patient-reported symptom outcomes in the five-days following Paxlovid prescription were determined by a follow-up telephone call.

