### 9.2.2. Exclusion Criteria

**There are no exclusion criteria for this study.**

## 9.3 Variables

The following variables are used to obtain comprehensive descriptive results.

1. Demographics
2. Date of symptoms
3. Viral variant analysis where available (type of viral variant ie, omicron, delta etc.)
4. PCR date along with CT Value

5. Co-morbidities and
6. BMI if  $\geq 30$
7. Symptoms at presentation
8. COVID 19 vaccine status (NB 92% of population has been vaccinated -with at least one dose of COVID 19 vaccine- in Bahrain)
9. Hospital admission
10. Follow up looking at compliance and reason of non-compliance
11. Day 5,7, 21 and 28 symptoms for COVID-19 patients who receive and HRU limited to admission (ICU, ward, need for oxygen therapy) or death
12. Date of symptoms resolution if applicable

**Table 2** Table 2 below depicts the patient demographics that will be accessed during the baseline and follow-up periods. The baseline period is defined as one year before the index date. Comorbidities (full list in [Table 6](#)) and maintenance medication usage for chronic conditions (eg, statins, antihypertensives, etc.) will be described during the baseline period and follow-up periods and are listed in [Table 3](#).

Risk factors for severe COVID-19, intensive care unit (ICU) usage, invasive mechanical ventilation (IMV) usage, supplemental oxygen use, non-invasive ventilation, and high-flow nasal cannula usage are depicted in [Table 5](#) and will be extracted from the *I-Seha* national electronic health record database.

Where applicable, emerging treatment patterns may be assessed as the time from symptom onset to COVID-19 diagnosis, time from symptom onset to treatment initiation, and the time from COVID-19 diagnosis to treatment initiation as illustrated in [Table 5](#).

10Nov23 WHO recommendations for Paxlovid treatments to define: 1. COVID-19 patients who meet the WHO criteria for “strongly recommended” 2. COVID-19 patients who meet the WHO criteria for “conditionally recommended”, and 3. COVID patients who are not falling into categories 1 or 2 will be used.

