**Table 2. Patient Demographic and Clinical Characteristic Variables at Index**

Variable	Operational definition
Age	Age will be defined as of the index date and will be used to assign patients to age groups: 18-29, 30-49, 50-64, 65-74, $\geq 75$ years and unknown/missing age.
Gender	Defined as of the index date as the distribution of female, male and unknown/missing sex patients.
Region	Kingdom of Bahrain
Nationality	Nationality of the patient will be mentioned
Enrollment Date Place of Service (POS)	Distribution of patients by the type of outpatient encounter during the enrollment date (eg, office visit, emergency room (ER), outpatient hospital, other, etc.).
Enrollment Date	Date (defined as MM/YYYY) of the enrollment date specified for each Cohort.

Variable	Operational definition
Specialty of Provider at enrollment Date	Distribution of the provider specialties present during the enrollment date. Patients with no provider specialty recorded will be included in an “Unknown/missing specialty” category.
Patient-reported COVID-19 symptoms	
List of COVID-19 symptoms to be added by study team (US, CDC definition).
 
1- Stuffy or runny nose 2- Sore throat 3- Shortness of breath 4- Cough 5- Low energy/tiredness/fatigue 6- Muscle ache/body aches 7- Headache 8- Chills or shivering 9- Feeling hot/feverish 10- Nausea or vomiting 11- Diarrhea 12- Loss of sense of smell 13- Loss of sense of taste

COVID-19 Symptom Onset Date	Date of symptom onset during the post-Paxlovid™ availability timeframe.
Time to COVID-19 Symptom Resolution	The number of continuous days with the same COVID-19 symptom. When available, the number of consecutive days will be reported as counts and percentages. The date of symptom resolution (last date recorded) will be reported when available.
Date of COVID-19 Vaccination	Date of each COVID-19 vaccination received. Note: patient-specific vaccination history may require more than 6-months pre-index time period.
Date of Paxlovid™ prescription written and/or fill history (eg, prescription claim)	Date of Paxlovid™ prescription written or fill history. Note: if both dates are available within the database, use the most recent date provided.

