## 1.2 STUDY OBJECTIVES

The overall aim of this study is to examine the baseline demographic, clinical, and outcome characteristics of COVID-19 patients who received Paxlovid.

PFIZER CONFIDENTIAL

CT24-WI-GL03-RF03 2.0 *Non-Interventional Statistical Analysis Plan For Secondary Data Collection*  
*Study 01-Jun-2020*  
Page 6 of 22

The objectives are

- (i) to describe the demographic, clinical, and outcome characteristics of COVID-19 patients who received Paxlovid and COVID-19 patients who were offered, but refused Paxlovid
- (ii) to examine differences in the demographic characteristics (e.g., age, sex, nationality, type of outpatient encounter, vaccination status) between COVID-19 patients who received Paxlovid and COVID-19 patients who refused Paxlovid,
- (iii) to examine differences in the clinical characteristics (e.g., comorbidities, symptoms, duration of symptoms) between COVID-19 patients who received Paxlovid and COVID-19 patients who refused Paxlovid over a five-day follow-up,
- (iv) to examine differences in outcomes (e.g., hospitalisations, time spent in an intensive care unit, time spent with invasive mechanical ventilation, supplemental oxygen usage, re-admission to hospital, deaths) between COVID-19 patients who received Paxlovid and COVID-19 patients who refused Paxlovid over a five-day follow-up.
- (v) To examine differences in the proportion of COVID-19 patients who meet the most up-to-date WHO recommendations for the use of therapeutics in the treatment of COVID-19 (ie, version 14, published 10Nov2023) in comparison to Kingdom of Bahrain national recommendations.

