**Table 1: Patient Demographic Variables**

Variable	Operational definition
Group	Received Paxlovid or did not receive Paxlovid
Age	Age will be defined as of the date of COVID-19 diagnosis using a PCR test and will be used to assign patients to age groups: 18-29, 30-49, 50-64, 65-74, $\geq 75$ years and unknown/missing age
Sex	Female, male and unknown/missing sex patients
Nationality	Nationality of the patient (Bahrain, other Middle East and North Africa, India, Pakistan, South East Asia, Caucasian)
Enrollment Date Place of Service (POS)	Type of outpatient encounter during the enrollment date (e.g., office visit, emergency room (ER), outpatient hospital, other, etc.)
Enrollment Date	Date (defined as MM/YYYY) of the enrollment date specified
Specialty of Provider at enrollment Date	Provider specialties present during the enrollment date. Patients with no provider specialty recorded will be included in an “Unknown/missing specialty” category
COVID-19 Symptom Onset Date	Date of symptom onset prior to presentation to healthcare facility

PFIZER CONFIDENTIAL

CT24-WI-GL03-RF03 2.0 *Non-Interventional Statistical Analysis Plan For Secondary Data Collection*  
*Study 01-Jun-2020*  
 Page 8 of 22

Time to COVID-19 Symptom Resolution	Time from onset of COVID-19 symptoms to resolution of symptoms
Date of COVID-19 Vaccination	Date of each COVID-19 vaccination received. Note: patient-specific vaccination history may require more than 6-months pre-index time period.
Date of Paxlovid prescription written and/or fill history (e.g., prescription claim)	Date of Paxlovid prescription written or fill history. Note: if both dates are available within the database, use the most recent date provided.

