## **HANDLING OF MISSING VALUES**

Missing data patterns, including the amount of missing data for each variable and individual and possible reasons for missing data, will be explored. As this is a descriptive study, missing data will not be imputed. The number and percentage of patients with missing data will be reported for each variable.

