### Inferential statistics

Between-group differences in categorical variables will be examined using proportions tests, Chi-square tests of independence or Fisher exact tests as appropriate. Differences in continuous variables will be examined using independent t-tests.

Differences in proportions or means (as appropriate) and 95% confidence intervals between COVID-19 patients taking Paxlovid, and COVID-19 patients who were offered Paxlovid therapy but who refused treatment will be reported. Additionally, Cramer's V or Cohen's d will be reported.

Cramer's V is a measure of association that quantifies the strength and direction of the relationship between the two categorical variables being compared. Cramer's V ranges from 0 to 1, where 0 indicates no association between the variables, and 1 represents a perfect association. The magnitude of Cramer's V will be interpreted as follows:

Cramer's V	Effect Size
-------------------	--------------------

0.1	Weak
0.3	Medium
0.6	Large

Cohen's d quantifies the standardized difference between the means of the two groups, and is calculated by taking the difference between the means of the two groups and dividing it by the pooled standard deviation. The magnitude of Cohen's d will be interpreted as follows:

Cohen's d	Effect Size
------------------	--------------------

0.2	Small
0.5	Medium
0.8	Large

An a priori alpha level of 0.05 has been selected for all tests. As this work is exploratory no adjustment for multiple comparisons will be made.

PFIZER CONFIDENTIAL

CT24-WI-GL03-RF03 2.0 *Non-Interventional Statistical Analysis Plan For Secondary Data Collection*  
Study 01-Jun-2020  
Page 14 of 22

Selection of the control groups will consider the following characteristics based on the availability of data using propensity-score matched:

- age,
- sex,
- COVID vaccination status,
- high-risk status for severe COVID-19 outcomes (WHO definition),
- assessment of healthcare seeking behavior in 365 days prior to COVID infection (such as flu or streptococcus pneumoniae vaccine, has primary healthcare provider, number of primary care/hospital visits),
- socioeconomic factors (such as household income, employment status),
- geographic location of residence,
- comorbidities.

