**LIST OF TABLES AND TABLE SHELLS****Table 3: Descriptive statistics for baseline variables**

Variables	Group		P-value	Effect size
	Paxlovid	Control		
Age, % (n)				
18-29				
30-49				
50-64				
65-74				
≥75 years				
Gender, % (n)				
Male				
Female				
Nationality, % (n)				
Bahrain				
Other Middle East and North Africa				
India				
Pakistan				
South East Asia				
Caucasian				

PFIZER CONFIDENTIAL

CT24-WI-GL03-RF03 2.0 *Non-Interventional Statistical Analysis Plan For Secondary Data Collection Study* 01-Jun-2020  
 Page 16 of 22

Enrollment Date Place of Service (POS), % (n)				
Office visit				
Emergency room				
Outpatient hospital				
Other				
Specialty of Provider at enrollment Date				
Interns				
Residents				
Family Phyiscans				
Specialist				
Consultants				
Number of days from COVID-19 symptom onset to resolution, mean (SD)				
Number of days from vaccination to contracting COVID-19, mean (SD)				
Number of days from contracting COVID-19 to being prescribed Paxlovid, mean (SD)				
Number of days from COVID-19 test to Paxlovid treatment, mean (SD)				
COVID-19 Lab Tests with Positive Result, % (n)				
COVID-19 Lab Test with Variant Type, % (n)				

PFIZER CONFIDENTIAL

CT24-WI-GL03-RF03 2.0 *Non-Interventional Statistical Analysis Plan For Secondary Data Collection Study* 01-Jun-2020  
 Page 17 of 22

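### The SAP follows patient-reported symptoms for five days after prescription but reports mean days from onset to resolution with no censoring rule; if that call is the only source of resolution dates, the treated group's duration is biased short

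*SAP*

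**What the plan says.** The SAP's Data source text gives the origin of symptom outcomes: "Patient-reported symptom outcomes in the five-days following Paxlovid prescription were determined by a follow-up telephone call". Objective (iii) in SAP 1.2 applies the same limit to "duration of symptoms) between COVID-19 patients who received Paxlovid and COVID-19 patients who refused Paxlovid over a five-day follow-up".

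SAP Table 1 defines the variable as "Time from onset of COVID-19 symptoms to resolution of symptoms", which is a time-to-event quantity with no stated cap. The shell for baseline variables (SAP Table 3) has the row "Number of days from COVID-19 symptom onset to resolution, mean (SD"), with P-value and effect-size columns. For analysis, "Differences in continuous variables will be examined using independent t-tests". For missing data, "As this is a descriptive study, missing data will not be imputed", although the number and percentage missing will be reported for each variable. No rule says what to do with a patient whose symptoms have not resolved at the last contact.

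The protocol is wider. Table 1 sets a 28-day follow-up. Section 9.3 lists "Day 5,7, 21 and 28 symptoms for COVID-19 patients who receive" as well as a date of symptom resolution. Protocol Table 2 adds: "The date of symptom resolution (last date recorded) will be reported when available".

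**The concern.** A patient who still has symptoms at the call has no resolution date. Read as written, the SAP leaves that value missing, and the patient drops out of the mean. The protocol's bracketed phrase about the last date recorded suggests another route, in which the last contact date stands in for recovery. Either way an unfinished illness becomes a missing or shortened one.

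This affects the treated group's own estimate, before any comparison with refusers. The SAP's overall aim includes describing the outcomes of patients who received Paxlovid. A mean over patients who recovered within the window depends heavily on when observation stopped and cannot show slow recovery. The row also sits among baseline variables, although symptom resolution is observed after the index date.

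**Working it through.** The plan states no symptom-duration figure, so there is nothing of its own to reproduce. The check asks how far a five-day window could move the treated mean.

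**Inputs**
- Window: 5 days after prescription (SAP, Data source and objective iii).
- Lag from onset to prescription: assumed 2 days. The documents give none for this cohort. The last day observed is then day 2 + 5 = 7 of illness.
- Duration T from onset: assumed log-normal with log-SD s = 0.5 and true median m of 3, 4, 6, 8 or 10 days.
- Patients are still symptomatic when prescribed (T > 2).

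**Formulas**, with cut-off c:
- F(t) = Φ[(ln t − ln m)/s]
- M(t) = m·exp(s²/2)·Φ[(ln t − ln m − s²)/s], the part of the mean from durations up to t
- True mean = [m·exp(s²/2) − M(2)] / [1 − F(2)]
- Share resolved = [F(c) − F(2)] / [1 − F(2)]
- Mean among resolved = [M(c) − M(2)] / [F(c) − F(2)]
- Mean with unresolved patients entered at last contact = share × mean among resolved + (1 − share) × c

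**Worked case, m = 8, c = 7.** F(2) = 0.0028, F(7) = 0.3947, m·exp(0.125) = 9.065, M(2) = 0.0048, M(7) = 2.008.
- True mean = (9.065 − 0.0048)/0.9972 = 9.1 days
- Share resolved = 0.3919/0.9972 = 39%
- Mean among resolved = 2.003/0.3919 = 5.1 days, so 4.0 days short
- Last-contact mean = 0.393 × 5.11 + 0.607 × 7 = 6.3 days, so 2.8 days short

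**All medians** (days). The last column repeats the resolved-only calculation with c = 30, that is, 28 days after prescription.

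| True median | True mean | Resolved by day 7 | Mean among resolved (shortfall) | Last-contact mean (shortfall) | Resolved-only shortfall, c = 30 |
|---|---|---|---|---|---|
| 3 | 3.9 | 94% | 3.6 (0.3) | 3.8 (0.1) | 0.00 |
| 4 | 4.8 | 86% | 4.1 (0.7) | 4.5 (0.3) | 0.00 |
| 6 | 6.9 | 62% | 4.7 (2.2) | 5.6 (1.3) | 0.02 |
| 8 | 9.1 | 39% | 5.1 (4.0) | 6.3 (2.8) | 0.11 |
| 10 | 11.3 | 24% | 5.4 (6.0) | 6.6 (4.7) | 0.35 |

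Between medians of 6 and 10 the true mean rises by 11.3 − 6.9 = 4.4 days, while the mean among resolved rises by only 5.4 − 4.7 = 0.7.

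**Other shapes and lags.** With gamma or log-normal durations of mean 7, 10 or 14 days, coefficient of variation 0.5 or 0.7, and a lag of 1, 2, 3 or 5 days, 6% to 76% resolve by the call. The resolved-only mean is 1.4 to 10.3 days short, and the last-contact mean 0.7 to 8.6 days short. These means leave out the quick recoveries in the first two rows above, so these ranges are not lower bounds.

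**The case against.** The strongest reply is that the documents do not say the five-day call is the only source of resolution dates. SAP Table 1 puts no cap on the variable. The SAP's Endpoints section takes in health-record variables that match the protocol's requirements, where available. The protocol lists symptoms on days 7, 21 and 28 and a resolution date, and section 9.4.1 describes a symptom database and gives no day for the call. If later dates are held and used, the bias nearly vanishes. This stands, and it makes the point conditional. It does not remove the point, because objective (iii) itself limits symptom duration to five days and no rule covers unresolved patients or later contacts.

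Second, the protocol's last date recorded can mean the last date on which a symptom was recorded, which is a reasonable resolution date. That stands too: the phrase is ambiguous, not wrong.

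Third, the SAP permits a median for skewed data, and missing counts will be shown. But the shell fixes a mean, a median among resolved patients is truncated in the same way, and showing the loss does not correct the estimate.

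Fourth, this is one descriptive row in a study without hypotheses, and the protocol's primary objective concerns baseline characteristics. That limits the importance but does not make the figure right.

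**Conclusion.** The point holds conditionally. If resolution dates come only from the five-day call, the treated group's reported duration is too short whenever some patients are unresolved at that call. The direction does not depend on the assumed distribution; the size does. Under log-normal durations with log-SD 0.5 and a 2-day lag, the shortfall among resolved patients runs from about 0.3 days (median 3) to about 6 days (median 10). With capture to day 28 it is at most about 0.35 days over the medians tried.

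A reader might infer that only fast resolvers can contribute, that the mean is sure to be out by several days, or that it will look favourable whatever the true course. The documents do not support that: the protocol provides for later symptom data, and quick recovery leaves little to truncate. Nor does the point settle the direction of bias in the comparison with refusers, which depends on how their symptoms were ascertained. What is firm is an unreconciled five-day against 28-day window, a time-to-event variable summarised as a plain mean without a censoring rule, and a post-index outcome in a baseline table. The plan should be changed on these points, though the primary objective is unaffected.

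**What to change.** - **Window.** Reconcile the SAP's five-day symptom follow-up with the symptom days in protocol 9.3, and state which contacts and records supply resolution dates.
- **Table row.** Move it from the baseline table to the post-index outcomes. Report the number and percent with all symptoms resolved by day 5, and by days 7, 21 and 28 where recorded, with all contacted patients as denominator.
- **Duration.** Where later contacts exist, give a Kaplan-Meier median with unresolved patients censored at last contact. Otherwise report the proportion only, since a survival method cannot extend five-day data.
- **Wording.** Clarify that the last date recorded means the last date a symptom was recorded in a patient documented as resolved, not the last contact of an unresolved patient.

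The cost is SAP wording, a clarification in the protocol and a standard summary of data already held. The drawback is that the median may not be estimable if fewer than half have resolved by last contact, in which case the report should say so.

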## 1.2 STUDY OBJECTIVES

The overall aim of this study is to examine the baseline demographic, clinical, and outcome characteristics of COVID-19 patients who received Paxlovid.

PFIZER CONFIDENTIAL

CT24-WI-GL03-RF03 2.0 *Non-Interventional Statistical Analysis Plan For Secondary Data Collection*  
*Study 01-Jun-2020*  
Page 6 of 22

The objectives are

- (i) to describe the demographic, clinical, and outcome characteristics of COVID-19 patients who received Paxlovid and COVID-19 patients who were offered, but refused Paxlovid
- (ii) to examine differences in the demographic characteristics (e.g., age, sex, nationality, type of outpatient encounter, vaccination status) between COVID-19 patients who received Paxlovid and COVID-19 patients who refused Paxlovid,
- (iii) to examine differences in the clinical characteristics (e.g., comorbidities, symptoms, duration of symptoms) between COVID-19 patients who received Paxlovid and COVID-19 patients who refused Paxlovid over a five-day follow-up,
- (iv) to examine differences in outcomes (e.g., hospitalisations, time spent in an intensive care unit, time spent with invasive mechanical ventilation, supplemental oxygen usage, re-admission to hospital, deaths) between COVID-19 patients who received Paxlovid and COVID-19 patients who refused Paxlovid over a five-day follow-up.
- (v) To examine differences in the proportion of COVID-19 patients who meet the most up-to-date WHO recommendations for the use of therapeutics in the treatment of COVID-19 (ie, version 14, published 10Nov2023) in comparison to Kingdom of Bahrain national recommendations.

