## Kingdom of Bahrain:

Kingdom of Bahrain is one of the leading countries in COVID-19 outpatient treatment care. A unique outpatient clinic has been established in May 2021 to provide outpatient care for patients with positive Coronavirus. Treatment including monoclonal antibodies such as Bamlamivimab, Regen-Cov, Sotorovimab and Paxlovid™ are offered for all high-risk and close contact patients, such treatments are in line with the guidelines of the FDA.

The clinic has a dedicated call center providing different services to ease the patient treatment process and provides follow-up care. The overall aim of the clinic is to target mild to moderate high risk COVID-19 patients and provide outpatient treatment as early as possible to reduce disease progression, including hospitalization and death.

On 01 January 2022, the National Health Regulatory Authority (NHRA) approved the emergency use of Paxlovid™ for mild-moderate cases who are at high risk – identified as per WHO definition of high-risk group – of developing severe COVID-19. Since approval, Paxlovid™ has been established as the first line therapy along with Sotrovimab in the Kingdom of Bahrain.

In the EPIC-HR trial, Paxlovid™ reduced the risk of hospitalization or death by 88% compared to placebo in non-hospitalized adults with laboratory-confirmed SARS-CoV-2 infection and a risk factor for progression to severe disease, when treatment was initiated within 5 days of symptom onset. Other efficacies reported for COVID-19 therapies, include sotrovimab (ie, 85% relative reduction reported), and remdesivir (ie, 87% relative reduction reported) and molnupiravir (ie, 30% relative reduction reported). Furthermore, *in vitro* analyses, suggested that Paxlovid™ is active against the B.1.1.529 (Omicron) variant of concern (VOC).

COVID-19 has put significant pressure on the healthcare system worldwide and caused an enormous economic burden to society. While patient characteristics, healthcare resource utilization (HRU) and healthcare costs of patients hospitalized with COVID-19 have previously been described in US studies, such data are limited among non-US countries. Furthermore, while the majority of current research focuses on hospitalized COVID-19 patients, little is known about COVID-19 patients identified in an outpatient setting.

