#### 9.4.1. EHR Database

There is a database of all patients who were eligible for Paxlovid™ therapy and details of those that accepted Paxlovid™ therapy and those that did not. Data on these patients that were treated with Paxlovid™ therapy and those that did not will be extracted from the I-Seha EHR. A retrospective review will be undertaken of patients symptom database to discern patient-reported symptoms (eg, time from onset, duration, severity, frequency) will be described in this study. Following Paxlovid™ treatment initiation, patients were followed up by a telephone call, regarding their symptom onset and severity; review of this standard of care data will be used to complement emerging treatment patterns and clinical characteristics throughout this study. For those that did not take Paxlovid™ treatment, data will be extracted by the CRAs from the EHR on patient reevaluation in a healthcare facility, admission to hospital or death.

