## 9.6. Data Management

EHR data will be obtained via a retrospective review of participant charts and used to discern participant-reported symptom onset, symptom duration, and relevant laboratory findings for diagnostic criteria or other related information described in [Table 2](#) and [Table 3](#).

The unstructured data that is extracted will be put into the eCRF, will then be anonymized by the clinical research assistants and presented in the format requested by the statistician at the time of analysis.

The study will abide to European GDPR legislation for maintaining confidentiality of data.

A Data Protection Impact Assessment (DPIA) will be performed to help identify and minimize the data protection risks of the study.

The EHR database is unstructured data. Individual medical records will be extracted and anonymized and populated into an eCRF. All data will be kept securely. Details of outcome measures and adverse events will be documented in hospital healthcare records. Individual research participant data is stored in an encrypted electronic database. The study investigators will adhere to hospital protocols pertaining to healthcare record use and storage to protect the research participant's identity, a unique identification code will be assigned by the Investigator, or authorized designee, to each study participant. These will be used in lieu of the participant's name, and the unique individual study code for each participant will be used for adverse events reporting and/or other study related data to be reported. This coded form of identification, instead of the participant's name, will appear on all documents/databases and will be cross-referenced by the participants date of birth (month/year). This server has managed access and password protection. The information that this server contains is backed up every 24 hours.

Personal information will be treated as confidential, but may need to be reviewed by authorized representatives of the Sponsor (such as monitors and auditors), the Contract Research Organization, the ethics committee and the regulatory authorities. The investigators and authorized designees will ensure that the confidentiality of the participants data is preserved.

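### The SAP tests symptom duration between treated patients and refusers, but the only symptom follow-up call described is the one made after Paxlovid

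*SAP*

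**What the plan says.** **The comparison.** SAP 1.2, objective (iii), covers "symptoms, duration of symptoms) between COVID-19 patients who received Paxlovid and COVID-19 patients who refused Paxlovid over a five-day follow-up". SAP Table 1 defines the variable as "Time from onset of COVID-19 symptoms to resolution of symptoms". The SAP Table 3 shell gives it a mean (SD) row with Paxlovid and control columns, a p-value and an effect size. The rule in SAP Inferential statistics is "Differences in continuous variables will be examined using independent t-tests", at alpha 0.05.

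**Symptom follow-up, treated patients.** SAP Data source: "Patient-reported symptom outcomes in the five-days following Paxlovid prescription were determined by a follow-up telephone call". Protocol 9.4.1 says that after treatment started, "patients were followed up by a telephone call, regarding their symptom onset and severity".

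**Follow-up, untreated patients.** The same Protocol section says that for these patients "data will be extracted by the CRAs from the EHR on patient reevaluation in a healthcare facility, admission to hospital or death". Symptoms are not on that list.

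**Sources not limited to one group.** Protocol 9.4.1 also plans a review of a symptom database that includes duration. Protocol 9.6 plans a chart review "used to discern participant-reported symptom onset, symptom duration, and relevant laboratory findings". Protocol section 7 adds: "The clinic has a dedicated call center providing different services to ease the patient treatment process and provides follow-up care".

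**Unresolved symptoms.** SAP Handling of Missing Values rules out imputation and promises missing counts, patterns and possible reasons. Protocol Table 2 defines time to resolution differently from the SAP, as a run of consecutive days with one and the same symptom, and glosses the resolution date as the last one on record.

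**The concern.** A between-group test of duration assumes that resolution was looked for in the same way and at the same times in both groups. As described, treated patients were telephoned and asked. Refusers' durations would come from whatever the records hold, and the follow-up named for them is contact with a facility, admission or death. If a recorded duration is more likely, or less likely, when illness lasts longer, the recorded means differ even when the true durations are identical.

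A five-day call also cannot see a resolution that comes later. A mean and t-test need a completed duration for every patient they include, and the plan does not say what happens to those without one.

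At stake is one exploratory row in a study of the sponsor's own product, where a spurious difference could be read as benefit or harm. The primary objective is not affected.

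**Working it through.** The documents give no SD, detectable difference or power for symptom duration, so there is no figure to reproduce. The check is first textual, then illustrative.

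**Step 1: ascertainment, side by side**

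| | Treated | Not treated |
|---|---|---|
| Symptom call after index | Described (SAP Data source; Protocol 9.4.1) | None described |
| Other named follow-up | Record extraction | Record extraction: re-evaluation, admission, death |
| Symptom database, charts | Not restricted by group | Not restricted by group |

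Protocol 9.3, item 11, attaches symptoms at days 5, 7, 21 and 28 to patients who receive something. The object of the verb is missing, so this is supporting evidence only.

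**Step 2: can existing safeguards remove the problem?** Reporting missing data by variable would reveal an imbalance but not correct it. The propensity score in SAP Inferential statistics uses baseline factors such as age, sex, vaccination and comorbidities. None describes how or when symptoms were recorded.

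**Step 3: unresolved patients.** With no imputation they may simply be missing. Under the Protocol Table 2 gloss they may enter with a duration cut off at the last recorded date. In the first case long illnesses are left out; in the second they are shortened. A mean with a t-test suits neither.

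**Step 4: illustration; every input is assumed**

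True duration X has the same distribution in both groups: gamma, mean 7 and SD 4 days, so shape (7/4)² = 3.0625 and scale 16/7 = 2.2857. Patients are still ill at prescription, L days after onset. Resolution is seen up to H days later, in both groups. Refuser capture is proportional to X^a.

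- Treated mean: E[X | L < X ≤ L+H].
- Refuser mean: E[X^(1+a)] / E[X^a], under the same condition.

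With a = 1 and unresolved patients left out:

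| L | H = 5: treated, refuser, gap | Treated with a date | H = 21: treated, refuser, gap |
|---|---|---|---|
| 2 | 4.60, 5.01, 0.41 | 55% | 7.26, 9.19, 1.93 |
| 3 | 5.41, 5.77, 0.36 | 61% | 7.73, 9.44, 1.71 |
| 5 | 7.19, 7.46, 0.27 | 69% | 9.04, 10.34, 1.29 |

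Variations, gap in days:

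- Other mean and SD pairs, (7,3), (7,5), (5,3) and (10,5), with a = 1: 0.26 to 0.45 at H = 5; 0.80 to 2.48 at H = 21.
- a = 0.5: 0.14 to 0.21 at H = 5; 0.61 to 0.95 at H = 21.
- a = 0 (capture unrelated to duration): 0.
- a = -0.5: -0.14 to -0.23 at H = 5; -0.54 to -0.88 at H = 21.
- a = 1, H = 5, unresolved patients entered at the last date: 0.55 to 0.64 instead of 0.27 to 0.41.

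**Step 5: would it reach p < 0.05?** For H = 5 with unresolved patients left out, and a two-sided test (assumed; the SAP does not state sides), the gap needed is 1.96 × √(SDt²/nt + SDr²/nr). Here nt = 3000 × share dated = 1656, 1840, 2074, and nr is an assumed number of refusers with a date.

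- L = 2, nr = 200: 1.96 × √(1.373²/1656 + 1.297²/200) = 0.19. The a = 1 gap of 0.41 exceeds it.
- L = 5, nr = 100: 1.96 × √(1.400²/2074 + 1.409²/100) = 0.28. The a = 1 gap of 0.27 falls just short.
- a = 0.5, nr = 100: gaps of 0.14 to 0.21 against 0.27 to 0.28; short at every lag.
- a = 0.5, nr = 200: gaps of 0.21, 0.18, 0.14 against about 0.20; reached only at L = 2.
- If matching left 1000 treated patients (assumed), the a = 1 thresholds rise to 0.28–0.30, 0.21–0.22 and 0.16 for 100, 200 and 500 refusers.

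**Step 6: a second illustration by simulation.** Gamma, mean 8 and SD 4 days in both groups; 3000 treated, all recorded; about 300 of 1000 refusers recorded. If shorter and longer illnesses are each recorded 30% of the time, the t-test rejects in 6% of runs. At 25% against 35%, the spurious gap is 0.5 days and it rejects in 53%. At 20% against 40%, the gap is 1.0 day and it rejects in 99.5%.

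**The case against.** Refusers may well have durations: the symptom database, the chart review and the call center are not restricted to treated patients. This stands. A reader might infer that controls have no symptom data, and the documents do not support that. What is missing is any description of equivalent follow-up.

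The work is labelled exploratory, sets no hypotheses or decision rules, extracts variables only if available, and limits its claims to association. It also promises to explore patterns of, and reasons for, missing data. All true, and this limits the consequence. It does not make unlike measurements comparable, and the row still carries a p-value and an effect size.

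A reader might also infer that unresolved patients necessarily drop out of the mean. No section says so, and the Protocol Table 2 gloss allows a truncated value instead. What can be said is that the handling is unspecified.

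Finally, the illustration assumes its inputs and gives both groups the same observation window, so it models selective recording and not the full contrast between a call and passive records. That is fair. The finding rests on the text, not on those figures.

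**Conclusion.** The point holds for one exploratory comparison and should be fixed. The plan tests symptom duration between groups while describing active symptom follow-up for one of them only, and it leaves unresolved patients undefined. The two definitions of duration, in Protocol Table 2 and SAP Table 1, also differ.

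The size and sign of any artefact cannot be derived from the documents. On the assumed inputs it runs from -0.88 to +2.48 days across all cases, and is zero if recording does not depend on duration. A reader might infer that the artefact will be significant, or that it will favour Paxlovid. Neither follows: some plausible cases cross the threshold, others do not, and the sign reverses if shorter illnesses are recorded more often.

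The conclusion rests on reading the silence about refusers as no description of equivalent follow-up. If refusers were in fact contacted in the same way and at the same times, saying so would settle the comparability question and leave only the handling of unresolved patients and the definition.

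**What to change.** 1. In SAP Data source, state for each group where post-index symptom data come from and on which days they were collected.
2. In the Table 3 duration row, show by group the number of patients with a recorded resolution date.
3. Unless refusers were followed in the same way and at the same times, remove the p-value and effect size from that row and report duration descriptively within each group, with a note that the groups are not comparable. The control column can stay, because SAP objective (i) describes both groups.
4. Use one definition of duration in both documents. Treat patients unresolved at last contact as censored, for example with a Kaplan-Meier median, in place of a mean and t-test.

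The cost is wording in SAP Data source, objective (iii) and the duration definition, one table row and one changed summary method. No new data are needed. The downside is that one exploratory between-group test may be given up.

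The SAP's five-day horizon against the Protocol's 28-day follow-up is a separate point that also needs reconciling.
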